7 DISCONTINUATION OF STUDY INTERVENTION AND PARTICIPANT DISCONTINUATION/WITHDRAWAL

7.1 DISCONTINUATION OF STUDY INTERVENTION

7.1.1 Permanent discontinuation

Study intervention should be permanently discontinued in any of the following cases:

- At the participant's request, at any time and irrespective of the reason (consent's withdrawal), or at the request of their legally authorized representative (if allowed by local regulations). "Legally authorized representative" is considered to be an individual or judicial or other body authorized under applicable law to consent on behalf of a prospective participant to the patient's participation in the procedure(s) involved in the research.
- If, in the Investigator's opinion, continuation of the study treatment would be detrimental to the participant's wellbeing, such as:
 - Unacceptable AE.
 - Documented disease progression.
 - Poor compliance to the study protocol.
 - Completion of 35 cycles when applicable.
 - Other, such as concurrent illness, that prevents further administration of study intervention, or that in the Investigator's opinion, in the best interest of the participant.
- In case of pregnancy occurrence.

If study intervention is permanently discontinued, the participant will remain in the study to be evaluated for serial tumor assessment if permanent discontinuation is not due to PD, for safety assessment as per SoA ([Section 1.3](#)) and until resolution or stabilization of AE, and any other assessment as per SoA. Data to be collected at the time of discontinuation of study intervention and follow-up and for any further evaluations that need to be completed are reported in the SoA.

7.1.1.1 ***Unacceptable adverse events leading to permanent intervention discontinuation***

Discontinuation of study intervention for abnormal liver function should be considered by the Investigator when a participant meets one of the conditions outlined in the dose modification and toxicity management guidelines (see individual substudy protocols), or if the Investigator believes that it is in best interest of the participant.

If a clinically significant finding is identified (including, but not limited to changes from baseline in QT interval corrected using Fridericia's formula [QTcF]) after enrollment, the Investigator or qualified designee will determine if the participant can continue in the study and if any change in participant management is needed. This review of the ECG printed at the time of collection must be documented. Any new clinically relevant finding should be reported as an AE.

Any potentially clinically significant abnormal laboratory value or ECG parameter will be immediately rechecked for confirmation and repeated after 24 hours to document evolution before making a decision of permanent intervention discontinuation for the concerned participant.

Decision criteria for discontinuation following immune-mediated AEs are described in Section 6.5 of individual substudies (Guidelines for the management of IRR, CRS, ICANS, VLS).

If participants are clinically stable, and possibly deriving clinical benefit from therapy with minimal toxicity, they will be maintained on treatment.

See the SoA for data to be collected at the time of intervention discontinuation and follow-up and for any further evaluations that need to be completed.

Handling of participants after permanent intervention discontinuation

Participants will be followed-up according to the study procedures specified in this protocol up to the scheduled date of study completion, or up to recovery or stabilization of any AE to be followed-up as specified in this protocol, whichever comes last.

If possible, and after the permanent intervention discontinuation, the participants will be assessed using the procedure normally planned for the last dosing day with the IMP including a pharmacokinetics sample, if appropriate. Tumor assessment should be repeated if not done at the last cycle.

All cases of permanent intervention discontinuation must be recorded by the Investigator in the appropriate pages of the e-CRF when considered as confirmed.

7.1.2 Temporary discontinuation

Temporary intervention discontinuation may be considered by the Investigator because of suspected AEs or disruption of the clinical trial due to a regional or national emergency declared by a governmental agency ([Section 10.9](#)). For all temporary intervention discontinuations, duration should be recorded by the Investigator in the appropriate pages of the e-CRF.

7.1.3 Rechallenge

Re-initiation of intervention with the IMP will be done under close and appropriate clinical/and or laboratory monitoring once the Investigator has considered according to his/her best medical judgment that the responsibility of the IMP in the occurrence of the concerned event was unlikely and if the selection criteria for the study are still met.

Recommendations for rechallenge in the context of an epidemic/pandemic (eg, COVID-19) are included in Appendix 9 Contingency Measures for a regional or national emergency ([Section 10.9](#)) that is declared by a governmental agency.

7.2 PARTICIPANT DISCONTINUATION/WITHDRAWAL FROM THE STUDY

- A participant may withdraw from the study at any time at his/her own request, or may be withdrawn at any time at the discretion of the Investigator for safety, behavioral, or compliance reasons. This is expected to be uncommon.
- At the time of discontinuing from the study, see SoA for data to be collected at the time of study discontinuation and follow-up and for any further evaluations that need to be completed.
- The participant will be permanently discontinued both from the study intervention and from the study at that time.
- If the participant withdraws consent for disclosure of future information, the Sponsor may retain and continue to use any data collected before such a withdrawal of consent.
- If a participant withdraws from the study, he/she may request destruction of any samples taken and not tested, and the Investigator must document this in the site study records.

If participants no longer wish to take the IMP, they will be encouraged to remain in the study.

The Investigators should discuss with them key visits to attend. The value of all their study data collected during their continued involvement will be emphasized as important to the public health value of the study.

Participants who withdraw from the study intervention should be explicitly asked about the contribution of possible AEs to their decision, and any AE information elicited must be documented.

All study withdrawals should be recorded by the Investigator in the appropriate screens of the e-CRF and in the participant's medical records. In the medical record, at least the date of the withdrawal and the reason should be documented.

In addition, a participant may withdraw his/her consent to stop participating in the study. Withdrawal of consent for intervention should be distinguished from withdrawal of consent for follow-up visits and from withdrawal of consent for non-participant contact follow-up, eg, medical record checks. The site should document any case of withdrawal of consent.

Participants who have withdrawn from the study cannot be re-included in the study. Their inclusion and intervention numbers must not be reused.

7.3 LOST TO FOLLOW UP

A participant will be considered lost to follow-up if he or she repeatedly fails to return for scheduled visits and is unable to be contacted by the study site.

The following actions must be taken if a participant fails to return to the clinic for a required study visit:

- The site must attempt to contact the participant and reschedule the missed visit as soon as possible and counsel the participant on the importance of maintaining the assigned visit schedule and ascertain whether or not the participant wishes to and/or should continue in the study.
- Before a participant is deemed lost to follow up, the Investigator or designee must make every effort to regain contact with the participant (where possible, 3 telephone calls and, if necessary, a certified letter to the participant's last known mailing address or local equivalent methods). These contact attempts should be documented in the participant's medical record.
- Should the participant continue to be unreachable, he/she will be considered to have withdrawn from the study.

Discontinuation of specific sites or of the study as a whole are handled as part of Appendix 1 (see [Section 10.1.9](#)).

8 STUDY ASSESSMENTS AND PROCEDURES

- Study procedures are summarized in this section and their timing is presented in the SoA ([Section 1.3](#)). Protocol waivers or exemptions are not allowed.
- Adherence to the study design requirements, including those specified in the SoA, is essential and required for study conduct.
- All screening evaluations must be completed and reviewed to confirm that potential participants meet all eligibility criteria. The Investigator will maintain a screening log to record details of all participants screened and to confirm eligibility or record reasons for screening failure, as applicable.
- Procedures conducted as part of the participant's routine clinical management (eg, blood count) and obtained before signing of the ICF may be utilized for screening or baseline purposes provided the procedures met the protocol-specified criteria and were performed within the time frame defined in the SoA.
- During the screening period, demography, medical/surgical, and disease history will be evaluated. Demography includes age, gender, race, and ethnicity. Medical/surgical history includes relevant history of previous pathologies and smoking status. Disease history includes stage at diagnosis and at study entry, and previous anti-tumor therapy (type, duration, reason for discontinuation and response to the therapy). In addition, results of driver gene mutation are also to be collected.
- A comprehensive medical history will be assessed for any cardiovascular signs or symptoms prior to treatment, along with a baseline ECG, echocardiography and troponin level.
- Regular blood samples will be collected from each participant throughout the duration of the study. Repeat or unscheduled samples may be taken for safety reasons or for technical issues with the samples. Details on blood sampling, including the estimated volume collected for each analysis are provided in the laboratory manual.
- For a regional or national emergency declared by a governmental agency, contingency measures are included in [Section 10.9](#).

8.1 EFFICACY ASSESSMENTS

The assessment of anti-tumor activity documented by objective response to the IMP is the primary endpoint for this study and is conducted as per schedule provided in the SoA. All participants treated must have at least one measurable lesion for inclusion.

Decision to pursue treatment will be based on the response evaluation made by the Investigator. A partial or complete response must be confirmed on a second examination done at least 4 weeks apart, in order to be documented as a confirmed response to therapy. Confirmation of PD may be done at the discretion of the Investigator when clinically indicated.

Investigators will obtain copies of the images and will provide them to Sponsor or other repository facility identified by the Sponsor for potential central review. Study sites must retain tumor assessment images, as Sponsor may decide to collect these images for possible Independent Central Review in the future.

Assessment of tumor response will be conducted using Response Evaluation Criteria in Solid Tumors (RECIST) 1.1 (see [Section 10.8](#)) according to the nature of the measurable lesions, as described below.

8.1.1 Assessment of objective response using the most appropriate modality according to the nature of the measurable lesion(s)

For participants with disease that is measured radiologically according to RECIST 1.1 criteria (see [Section 10.8](#)), a CT or MRI for tumor assessment will be performed as detailed in [Section 1.3](#). The choice of whether the imaging is by CT (preferred) or MRI is an Investigator decision. Once the choice of CT scan or MRI has been made, the same imaging technique should be used in a participant throughout the trial.

Baseline imaging should include all known target lesions. Baseline scans must evaluate extent of disease, including imaging of chest, abdomen, and pelvis and any other locations with suspicion or evidence of disease involvement. This may be accomplished with CT chest, abdomen, and pelvis with contrast, or CT chest with contrast and MRI abdomen/pelvis with gadolinium.

The initial CT/MRI tumor imaging will be performed within 28 days prior to C1D1. Scans performed as part of routine clinical management are acceptable for use as the screening scan if they are of diagnostic quality and performed within 28 days prior to the date of enrollment. On study imaging will be performed every 9 weeks (63 ± 7 days) after the date of first IMP and if clinically indicated. Imaging studies should follow calendar days and should not be adjusted for delays in cycle starts or extension. After Week 45 tumor imaging should be performed every 12 weeks (84 ± 7 days). Per the primary tumor assessment criteria, after the first documentation of response or the first documentation of progression (if the participant is clinically stable), confirmatory imaging may be performed no fewer than 28 days later. Alternately, the scan performed at the next scheduled time point (eg, every 63 ± 7 days) may be used as confirmation. Tumor assessment is not needed for participants who start another anticancer therapy.

For participants with no previous history of brain metastases, screening brain imaging will need to be obtained. MRI is the preferred imaging modality however CT is acceptable if an MRI is clinically contraindicated. If lesions are identified, the lesions must be treated, regardless of symptoms. Two additional scans, obtained at least 4 weeks apart, should be obtained to document disease stability AFTER local treatment administration to the brain metastases has been completed. If participants receive therapy during these 4 weeks stabilization at the treating physician's discretion, it will be considered as prior anticancer therapy. Participants with previously treated brain metastases may participate provided they are stable, which is defined as lack of progression on two sets of imaging obtained at least 4 weeks apart. Stability as defined above should be documented prior to the first dose of trial treatment. In addition, any neurologic symptoms must have returned to baseline or resolved, and the participant is not using steroids for at least 14 days prior to study treatment. The screening brain scan may be collected up to 42 days prior to enrollment.

RECIST 1.1

RECIST 1.1 will be used as the primary measure for assessment of tumor response, date of disease progression, and as a basis for all protocol guidelines related to disease status (eg, discontinuation of study intervention).

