- Incidence of treatment emergent adverse events (TEAEs), serious adverse events (SAEs), laboratory abnormalities according to National Cancer Institute Common Terminology Criteria for Adverse Events (NCI CTCAE) V5.0 and American Society for Transplantation and Cellular Therapy (ASTCT) consensus grading (2)
- Time to response (TTR), defined as the time from the first administration of investigational medicinal product (IMP) to the first tumor assessment at which the overall response was recorded as PR or CR that is subsequently confirmed and determined by Investigator per RECIST 1.1
- Duration of response (DoR), defined as the time from first tumor assessment at which the overall response was recorded as CR or PR that is subsequently confirmed until documented progressive disease (PD) determined by Investigator per RECIST 1.1 or death from any cause, whichever occurs first
- Clinical benefit rate (CBR) including confirmed CR or PR at any time or stable disease (SD) of at least 6 months determined by Investigator per RECIST 1.1.
- Progression-free survival (PFS), defined as the time from the date of first IMP administration to the date of the first documented disease progression determined by Investigator as per RECIST 1.1 or death due to any cause, whichever occurs first
- Plasma concentrations and where applicable PK parameters of SAR444245
- Incidence of anti-drug antibodies (ADAs) against SAR444245

For China, please see [Section 10.7](#) for details.

Overall design:

This is a Phase 2, multi-cohort, un-controlled, non-randomized, open-label, multi-center study assessing the antitumor activity and safety of SAR444245 combined with other anticancer therapies in participants with advanced or metastatic gastrointestinal cancer.

Brief summary:

A graphical presentation of the study schema is shown [Figure 1](#).

Special considerations pertaining to methodology

Interactive Response Technology (IRT) will be used to control recruitment, assignment per site and to facilitate the handling, management, and accountability of drug supply.

Number of participants:

Please refer to the individual substudy for the numbers of participants to be enrolled and treated at the recommended safe dose.

Note: Enrolled participants are all participants from screened participants who have been allocated to an intervention regardless of whether the intervention was received or not.

Intervention groups and duration:

The duration of the study for a participant will include:

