Cycle Day (Visit window in Days)	D-28 to D-1	D1	D8 ^f (±1)	D15 ^f (±1)	D1 (±3)	30 days (+/- 7 days) after last IMP or at initiation of further therapy	3 months after last IMP admin ±7 days	6 months after last IMP admin ±7 days	Every 3 months after FU visit 2 ± 7 days	Every 3 months +/- 14 days		
Urinalysis ^g	X	X			X	X	X				See Section 10.2	
IMP												
SAR444245		X			X							
Hospitalization ^h		X										
AE/SAE assessment ^k	X	Continuously throughout treatment period					X				See Section 8.3	
Prior/Concomitant Meds	X	Continuously throughout treatment period									See Section 6.8	
First subsequent anti-cancer therapy						X	X	X	X	X		
Survival status										X		
Pharmacokinetic (PK) / Pharmacodynamic (PDy) / Immunogenicity assessments												
PK SAR444245	See PK flowcharts in Section 1.5.1 and Section 1.5.2											
ADA SAR444245	See PK flowcharts in Section 1.5.1 and Section 1.5.2											
PDy - Blood and tumor tissue collection ^{l,m}	See Biomarker Flowchart in Section 1.4											
Tumor assessment												
Brain imaging ⁿ	X										See Section 8.1	
CT/MRI ^o	X				X	X	X	X	X		See Section 8.1	

- a Evaluation: Screening assessments to be performed prior to first IMP administration unless otherwise indicated. There is no need to perform Cycle 1 Day 1 laboratory assessments that have been performed as part of screening within 3 days prior to first IMP administration. During the study treatment period, all assessments must be performed, and results should be reviewed by the investigator prior to IMP administration at that visit. After Cycle 1, samples for laboratory assessments (excluding PK & biomarker) can be collected up to 3 days prior to IMP administration. ICF must be signed before any study-specific procedures are performed and can be signed more than 28 days prior to first IMP administration. Screening time indicates the maximum time frame relative to the first IMP administration in which study procedures used to support eligibility are done.
- b Cycle: a treatment cycle is 21 days. See details in [Section 6.1](#) for IMP administration. If treatment cycles are adjusted, all procedures except tumor assessment imaging will be completed according to the cycle number. Tumor assessment imaging will be performed at fixed time points from C1D1 regardless of any treatment delays.

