Target lesions: All measurable lesions up to a maximum of 2 lesions per organ and 5 lesions in total, representative of all involved organs, should be identified as target lesions and recorded and measured at baseline. Target lesions should be selected on the basis of their size (lesions with the longest diameter), be representative of all involved organs, but in addition should be those that lend themselves to reproducible repeated measurements. It may be the case that, on occasion, the largest lesion does not lend itself to reproducible measurement in which circumstance the next largest lesion which can be measured reproducibly should be selected. A sum of the diameters (longest for non-nodal lesions, short axis for nodal lesions) for all target lesions will be calculated and reported as the baseline sum diameters. If lymph nodes are to be included in the sum, then only the short axis is added into the sum. The baseline sum diameters will be used as reference to further characterize any objective tumor regression in the measurable dimension of the disease.

Non-target lesions: All other lesions (or sites of disease) including any measurable lesions over and above the 5 target lesions should be identified as non-target lesions and should also be recorded at baseline. Measurements of these lesions are not required, but the presence, absence, or in rare cases unequivocal progression of each should be noted throughout follow-up.

Methods for Evaluation of Measurable Disease

All measurements should be taken and recorded in metric notation using a ruler or calipers. All baseline evaluations should be performed as close as possible to the beginning of treatment and never more than 4 weeks before the beginning of the treatment.

The same method of assessment and the same technique should be used to characterize each identified and reported lesion at baseline and during follow-up. Imaging-based evaluation is preferred to evaluation by clinical examination unless the lesion(s) being followed cannot be imaged but are assessable by clinical exam.

Clinical lesions. Clinical lesions will only be considered measurable when they are superficial (eg, skin nodules and palpable lymph nodes) and ≥ 10 mm (≥ 1 cm) diameter as assessed using calipers (eg, skin nodules). In the case of skin lesions, documentation by color photography, including a ruler to estimate the size of the lesion, is recommended.

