Complete Response (CR): Disappearance of all target lesions. Any pathological lymph nodes (whether target or non-target) must have reduction in short axis to <10 mm (<1 cm).

Partial Response (PR): At least a 30% decrease in the sum of the diameters of target lesions, taking as reference the baseline sum diameters.

Progressive Disease (PD): At least a 20% increase in the sum of the diameters of target lesions, taking as reference the smallest sum on study (this includes the baseline sum if that is the smallest on study). In addition to the relative increase of 20%, the sum must also demonstrate an absolute increase of at least 5 mm (0.5 cm). (Note: the appearance of one or more new lesions is also considered progressions).

Stable Disease (SD): Neither sufficient shrinkage to qualify for PR nor sufficient increase to qualify for PD, taking as reference the smallest sum diameters while on study.

Evaluation of Non-Target Lesions

Complete Response (CR): Disappearance of all non-target lesions and normalization of tumor marker level. All lymph nodes must be non-pathological in size (<10 mm [<1 cm] short axis). Note: If tumor markers are initially above the upper normal limit, they must normalize for a patient to be considered in complete clinical response.

Non-CR/Non-PD: Persistence of one or more non-target lesion(s) and/or maintenance of tumor marker level above the normal limits.

Progressive Disease (PD): Appearance of one or more new lesions and/or unequivocal progression of existing non-target lesions. Unequivocal progression should not normally trump target lesion status. It must be representative of overall disease status change, not a single lesion increase.

Although a clear progression of “non-target” lesions only is exceptional, the opinion of the treating physician should prevail in such circumstances, and the progression status should be confirmed at a later time by the review panel (or Principal Investigator).

Evaluation of Overall Response Criteria

The best overall response is the best response recorded from the start of the treatment until disease progression/recurrence (taking as reference for progressive disease the smallest measurements recorded since the treatment started). The patient’s best response assignment will depend on the achievement of both measurement and confirmation criteria. Revised Response Evaluation Criteria in Solid Tumors (RECIST) Version 1.1 are summarized in the table:

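### Routine-care baseline CT/MRI scans are timed from enrollment, while the rest of the protocol times baseline imaging from first dose, so a scan older than 28 days at C1D1 can be accepted

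*Protocol*

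**What the plan says.** Two adjoining sentences in master protocol Section 8.1.1 set the age limit for the baseline tumor scan. The general one reads "The initial CT/MRI tumor imaging will be performed within 28 days prior to C1D1". The next lets a scan from routine clinical management serve as the screening scan if it is of diagnostic quality and was "performed within 28 days prior to the date of enrollment". The same pair stands in the CT/MRI footnote of the master SoA (Section 1.3, footnote o) and of the substudy 01 SoA (Section 1.3, footnote p).

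Other places bear on the same limit:

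- Appendix 8 (Section 10.8) says baseline evaluations are "never more than 4 weeks before the beginning of the treatment".
- The SoA screening column runs from D-28 to D-1, and footnote a gives its anchor: "Screening time indicates the maximum time frame relative to the first IMP administration in which study procedures used to support eligibility are done".
- Section 8 admits routine-care procedures as baseline "provided the procedures met the protocol-specified criteria and were performed within the time frame defined in the SoA". It also rules out waivers.
- The Synopsis counts a participant as enrolled once "allocated to an intervention regardless of whether the intervention was received or not".

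**The concern.** Enrollment and first dose are different events. By the Synopsis definition a participant can be enrolled before receiving any drug, and nothing in the text requires dosing on the same day or states how soon it must follow. A site that follows the routine-care sentence to the letter can therefore use a scan that breaks the C1D1 rule and the appendix.

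The baseline scan feeds the primary endpoint directly. Partial response is a fall of at least 30% in the diameter sum, "taking as reference the baseline sum diameters". Progression is judged against the smallest sum on study, which is the baseline until something smaller is seen. If the tumor grows between the scan and first dose, that growth is booked as change on treatment. It makes a response harder to reach and brings progression forward. The direction is conservative for ORR, but it would vary between participants with the age of their scan, for no reason connected to the drug.

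**Working it through.** **Step 1: age of the scan at first dose.** Let g be the number of days from enrollment to C1D1. The documents do not give g, so it is an assumption shown over a range.

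- C1D1 rule and Appendix 8: maximum age = 28 days, whatever g is.
- Routine-care sentence: maximum age = 28 + g days.

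The stated 28-day limit is reproduced only at g = 0. At g = 1 the maximum is 29 days, and the two rules already conflict. At g = 3, 7 and 14 it is 31, 35 and 42 days.

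**Step 2: interval to the first on-study scan.** Section 8.1.1 says "On study imaging will be performed every 9 weeks (63 ± 7 days) after the date of first IMP and if clinically indicated".

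- C1D1 rule: 28 + 63 = 91 days, or 98 with the +7-day window.
- Routine-care sentence with g = 7: 35 + 63 = 98 days, or 105 with the window.

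**Step 3: what the extra days do to a measured response.** The comparison is between a baseline at the permitted limit (28 days old) and one g days older. Assume the untreated diameter sum doubles every D days, with D from 90 to 180. This is an assumption; the documents give no growth rate. The older baseline is then smaller by a factor 2^(g/D). A follow-up sum at 0.70 of the 28-day-old baseline (exactly 30% shrinkage) becomes 0.70 × 2^(g/D) of the older one:

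| g (days) | Scan age at C1D1 | D = 180 days | D = 90 days |
|---|---|---|---|
| 3 | 31 | 0.708, reads as 29% shrinkage | 0.716, reads as 28% |
| 7 | 35 | 0.719, reads as 28% | 0.739, reads as 26% |
| 14 | 42 | 0.739, reads as 26% | 0.780, reads as 22% |

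Every cell falls below the 30% threshold, so a change that just qualifies against a compliant baseline does not qualify against the older one. Only changes close to the threshold are affected.

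**Step 4: the progression side.** While baseline is still the smallest sum, the 20% increase is reached once the sum is 1.20 / 2^(g/D) of the 28-day-old baseline. For g = 3, D = 180 this is 1.20 / 1.012 = 1.186. For g = 14, D = 90 it is 1.20 / 1.114 = 1.077. The relative criterion is thus met after 18.6% or 7.7% growth instead of 20%; the 5 mm absolute criterion must still be met.

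**Step 5: from participant to cohort.** Going further needs the share of participants with a routine-care scan, the age of those scans, the distribution of g, and how many changes lie near the threshold. None of these is in the documents, so no effect on ORR is computed.

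**The case against.** The strongest defense is that the protocol already controls this. The preceding sentence, the SoA screening window, footnote a and Appendix 8 all point to first dose, and Section 8 admits routine-care procedures only inside the SoA time frame. Read together, the enrollment sentence would be an extra condition and no accepted scan could be older than 28 days at C1D1.

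This shows that the enrollment anchor is the outlier, and that much stands. It does not remove the conflict. Section 8 sends the reader to the SoA, and the SoA's own CT/MRI footnote carries the enrollment wording. Nor would that wording do any work as an extra condition: a scan taken before enrollment and within 28 days of C1D1 is necessarily within 28 days of enrollment. A natural reading is that it relaxes the rule for routine scans.

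The point about weight also stands. An over-age baseline needs a routine-care scan, near the edge of the window, in someone enrolled at least a day before dosing. The analysis is descriptive. With about 40 participants in Cohort A, the 90% interval at 8 responders runs from 10.4% to 33.2% (substudy 01, Table 9). A 90-day doubling of diameters means roughly an eightfold volume increase (2³) in that time, so the 22% figure sits at the fast end of the assumption.

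Two stronger readings are tempting and not supported:

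- A reader might infer a definite loss, say one responder per cohort (1/40 = 2.5 points). Nothing in the documents supports that or any other bound.
- A reader might take Step 3 to mean that a true 30% shrinkage measured from first dose would read as 29% to 22%. It does not. On the same assumptions even a compliant 28-day-old scan would turn that shrinkage into 22% (0.70 × 2^(28/180) = 0.780) or 13% (0.70 × 2^(28/90) = 0.868). The table isolates only the days beyond the protocol's own limit.

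**Conclusion.** The inconsistency is real and stands in current text in Section 8.1.1, the master SoA and the substudy 01 SoA. It rests only on the difference between enrollment and first dose and does not depend on any growth assumption. Whenever enrollment precedes C1D1 by a day or more, a scan at the edge of the routine-care window breaches the first-dose limit. How often this would happen is unknown.

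The consequence is a small bias against response and toward earlier progression in the participants concerned: roughly 1 to 8 percentage points of apparent shrinkage for 3 to 14 extra days under the assumed doubling times. At cohort level it is probably small. It is a wording fault worth correcting because it touches the primary endpoint's reference measurement, and it does not undermine the design.

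**What to change.** In master protocol Section 8.1.1, in footnote o of the master SoA and in footnote p of the substudy 01 SoA, change the anchor for routine-care CT/MRI scans from the enrollment date to C1D1. Do the same in any other substudy schedule that repeats the sentence. Every baseline CT/MRI scan is then at most 28 days old at first dose whatever the enrollment gap, in line with SoA footnote a, Section 8 and Appendix 8. The screening brain scan has its own window and is not part of this edit.

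The cost is a wording change at the next amendment, plus an occasional repeat baseline scan for a participant whose routine scan has aged past 28 days by first dose.
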